6.1 PARTICIPANT TRACKING & CLINICAL MANAGEMENT

6.2 Retention Efforts

Study staff will track retention, which will be reviewed weekly by the PIs. As has been successful in previous studies with this population, including the MyPEEPS Mobile efficacy trial, we will: 1) obtain, at baseline, participants' email addresses, phone numbers, social media handles, as well as the addresses and contact information of people participants believe could help us locate them in the future; 2) allow for any time of day, and all days of the week, for participants to complete online assessment visits; 3) provide participants with numerous methods for contacting study staff, including providing study phone numbers, email addresses, and social media handles and if agreed to by the participant, having them program our site numbers into their mobile phone during the enrollment visit; 4) routinely verify participants' locator information at every contact point; 5) if correspondence is returned indicating a participant no longer has a given email address, study staff will telephone to obtain their new email address; 6) if the phone number is disconnected, we will contact them via their social media accounts and/or individuals listed in participants' records; and 7) if participants are not responsive after 5 email correspondence attempts and/or have given permission to message them via phone number, we will attempt to make contact using participants' phone numbers using IRB-approved scripts. We will make every effort to maintain contact with participants, even if they move or discontinue the intervention, for those still willing to complete follow-up assessment visits. Given the older study population proposed in this trial, we are confident we will retain at least 80% of the study population for this study proposed in this trial, we are confident we will retain at least 80% of the study population for this study.

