7.3.2 Data Management and Data Quality

Columbia University will be responsible for computerized survey programming, data capture, management, and analysis. All study information will be identified through the Participant Identification Number (PID) on all forms and computerized files. Data files will be exported from the ACASI program and imported into the SPSS database for storage. Computer data files never have any identifying information and are encrypted prior to transfer between study sites. Data entered into the SPSS database will not include any identifying information. Only authorized users with a login name and password will be able to open the computerized survey, and only those with administrative privileges will be able to access data. The study research assistant (RA) will use a login name and password to gain access to the software to administer it to a participant, but they will have no ability to access the saved data. The database, data structure, and data quality will be routinely reviewed by [name], and the Data Manager will set up the database, check data quality, and prepare the data for use. The Multiple PIs will work closely to plan analyses for various purposes, including for hypothesis testing and manuscript development and reports. Data quality will be examined before statistical analyses are conducted, including examination of missing data,

assessment of distributional assumptions, and identification of outliers. In addition to data quality, the comparability between intervention and control groups will be carefully examined, including baseline balance and differential attritions at all waves of follow-up. While differences are not expected from the randomized design, it is prudent to plan for this contingency so that sufficient follow-up data and appropriate statistical methods can be used for intent-to-treat analyses. The psychometric properties of instruments will also be examined, as will the patterns of missing data.

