Data Analysis. All multivariate analyses will be preceded by standard descriptive bivariate analyses to describe key variables and relationships among key variables. These analyses will include means, frequency tables, histograms, and examination of distributions. All statistical tests will be two-sided tests with the level of significance at 0.05(60).

Outcomes: This study will examine whether the intervention will reduce the number of condomless receptive anal or vaginal penile sex with either a cisgender male or transgender woman; the primary outcome is a count measure (Table 6 - Outcome Measures). We assume that all count outcome variables follow Poisson or negative binomial (NB) distribution, $y \sim \text{Poi}(\lambda)$ or $y \sim \text{NB}(\lambda, \kappa)$ and all percentage outcomes follow binomial distribution, $y \sim \text{bin}(n, p)$. Let the expected value of outcome, $E(y) = \varphi$, so $\varphi = \lambda$ for count outcomes and $\varphi = p$ for binary outcomes. We propose the following generalized linear mixed model (GLMM) to analyze all outcomes. The level of analysis

will be assessed at each data point. For person i and data assess wave W (i.e. baseline, 3, and 6 months):

$$+ \mu_i,$$

where $h(\cdot)$ is the link function for the GLMM. We will use log-links (Poisson or NB regression) for count

Table 7. Codes for design variables

Months	Intervention			Delayed Intervention		
	Arm	W	INT	Arm	W	INT
Baseline	0	0	0	1	0	0
3 mos	0	1	1	1	1	0
6 mos	0	2	1	1	2	1

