7.7 Missing Data

Missing data may occur in the proposed study in several ways. First, it may be due to item non-response. In these cases, we will prorate total scores for a measure by taking an average score on the measure and multiplying it by the total number of items in the scale. Attrition can result in missing data due to missed assessments or dropout from the study. Prior to performing any outcome analyses, we will evaluate the amount, reasons, and patterns of missing data. Missing data unrelated to the outcome of interest will be considered missing completely at random (MCAR), and complete case analysis will still generate unbiased estimates.(89) For the missing values at the baseline or partial baseline collected data, we will use a multiple imputation approach.(89) We will conduct sensitivity analyses to compare estimates of treatment effects with and without multiple imputation to assess the effect of missing data on statistical inference.

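### The only missing-data sensitivity check compares results with and without baseline imputation, so it is uninformative about outcome-related loss of the 3- and 6-month counts

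*Combined protocol and SAP*

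**What the plan says.** Section 7.7 (Missing Data) names two sources of missing data. Item non-response is handled by prorating scale scores. The other source is loss over time: "Attrition can result in missing data due to missed assessments or dropout from the study". For that loss, the team will look at amount, reasons and patterns before any outcome analysis. Where missingness is judged unrelated to the outcome, it says that "complete case analysis will still generate unbiased estimates". No rule is given for other kinds of dropout.

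Imputation is then defined for one case: "For the missing values at the baseline or partial baseline collected data, we will use a multiple imputation approach". The sentence that follows sets the robustness check: "We will conduct sensitivity analyses to compare estimates of treatment effects with and without multiple imputation to assess the effect of missing data".

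Elsewhere:
- Section 7.6 gives the main model: "We propose the following generalized linear mixed model (GLMM) to analyze all outcomes". It has a person-level random intercept and covers baseline, 3 and 6 months.
- Sections 7.3.2 and 7.3.3 promise a comparison of the arms, "including baseline balance and differential attritions at all waves of follow-up", and mention suitable intent-to-treat methods without naming any.
- Section 6.2 states the retention expectation, "we are confident we will retain at least 80% of the study population", and Table 5 repeats 80% as a feasibility threshold.
- Section 6.5 lists repeated non-compliance with the intervention, and a reported HIV-positive diagnosis, as reasons for leaving the study early. Section 6.4 ends data collection once a participant is permanently discontinued from the study.

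**The concern.** Under section 4.5, randomisation follows completion of the baseline assessment, so whole-visit loss at baseline should be rare. Follow-up is by emailed survey, and that is where most missing outcomes will arise. The plan imputes the first and not the second, yet gives the comparison the general task of showing what missing data do to inference.

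Some follow-up loss may well be related to outcome. Until month 3 only the intervention arm has the app, so removal for non-compliance with the intervention can act on one arm of the primary comparison. Loss after an HIV-positive report is plausibly linked to the behaviour being counted. Sections 6.4 and 6.5 together leave these later values unobserved.

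What is at stake is the effect size. Section 7.6 says the pilot estimates will be used to set the sample size of a later trial. An estimate too far from the null would make that trial too small, and the stated check would give no warning.

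**Working it through.** The plan gives no figure on this point to reproduce. The check has four steps.

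**1. What each missing-data provision covers.**

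| Missing item | Handling | Sensitivity analysis |
|---|---|---|
| Scale items | Prorated scores | None stated |
| Baseline values | Multiple imputation | With versus without imputation |
| 3- and 6-month counts | Mixed model on observed waves; complete cases if judged unrelated to outcome | None stated |

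The sensitivity analysis in section 7.6 concerns partners' PrEP use and viral suppression, not missing data.

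**2. Does the planned comparison respond to dropout?** If baseline is complete, imputation fills nothing in, and the two fits use the same data. A small simulation shows the consequence. It had 40 participants per arm, three waves and the intervention indicator of Table 7. It used a random-intercept linear model on a log-scale outcome as a stand-in for the count model, a true effect of ln(0.55), and 60 replicates per scenario. Variances and dropout mechanism are assumptions. In the outcome-related scenarios, intervention participants with high 3-month values were more likely to leave.

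| Scenario | With minus without imputation | Error against no-dropout fit (log scale, Monte Carlo SE) | Ratio with dropout / without |
|---|---|---|---|
| 20% random dropout, baseline complete | 0.000 | 0.004 (0.011) | 0.567 / 0.565 |
| 14% outcome-related dropout, baseline complete | 0.000 | -0.142 (0.012) | 0.449 / 0.518 |
| 14% outcome-related dropout, 5% of one baseline covariate missing | mean 0.0003, mean absolute 0.036 | -0.141 (0.011) | 0.487 / 0.561 |

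The comparison reads the same in the first two rows, although only the second is distorted. The direction is informative; the exact size is not.

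**3. Illustrative size.** Inputs are a ratio of 0.55 (section 7.6, given there as a hypothetical for the future trial) and the 20% maximum loss under the 80% target, which is 8 of 40 in the intervention arm. Assumed: k, the dropouts' mean count relative to the control mean, and control dropouts who resemble control completers. The documents give no value for k.

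Full-sample ratio = 0.8 × 0.55 + 0.2 × k
- k = 1.0: 0.44 + 0.20 = 0.64
- k = 1.5: 0.44 + 0.30 = 0.74
- ratio of 1.0 reached at k = (1 - 0.44) / 0.2 = 2.80

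If all 16 of the 80 losses fell in the intervention arm, the retained share there is 24/40 = 0.6. The ratio is then 0.33 + 0.4 × k: 0.73 at k = 1.0, 0.93 at k = 1.5, and 1.0 at k = 0.67/0.4 = 1.68.

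**4. Effect on the size of the future trial.** With constant variance on the log scale, required size is proportional to 1/(ln RR)².
- 0.64: (ln 0.55 / ln 0.64)² = 1.79
- 0.74: (ln 0.55 / ln 0.74)² = 3.94

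With Poisson variance proportional to 1 + 1/RR, the factors are 2.818 at 0.55, 2.563 at 0.64 and 2.351 at 0.74:
- 0.64: 1.79 × 2.563/2.818 = 1.63
- 0.74: 3.94 × 2.351/2.818 = 3.29

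**The case against.** A reader might infer that the plan ignores dropout or that its effect estimate is biased. The documents do not support that. A random-intercept model fitted by likelihood to all observed waves keeps participants with partial follow-up and is valid if dropout is missing at random. The complete-case remark applies to data judged unrelated to the outcome; it is not a general rule. Retention by arm and missing-data patterns will be examined, and section 6.2 keeps contact with people who stop the intervention but will still complete assessments. It is therefore speculation that a distorted estimate would pass unnoticed. These steps remain descriptive, however: none yields an effect estimate under a different dropout assumption.

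A reader might also infer that the planned comparison will always come out at zero. It need not. Participants may skip sensitive questions at baseline, and with 5% of one covariate missing the two estimates differed by 0.036 on average in absolute terms. That movement reflects baseline missingness and carries no information about dropout.

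The comparison sentence is not itself worded as limited to baseline. Even so, no other imputation is defined for it to refer to.

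The study is an 80-person pilot not powered for efficacy, and imputing follow-up under a missing-at-random assumption would largely repeat what the mixed model already assumes. Both points stand. They limit the severity and shape the remedy.

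**Conclusion.** The point holds as a gap in the robustness check. As written, section 7.7 has no analysis that could show sensitivity to outcome-related loss of 3- or 6-month counts, and the one check offered is uninformative about it. The validity of the mixed model under missing at random is not in dispute, provided it is fitted by likelihood to all available waves.

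The ratios 0.64 and 0.74, and the sample-size multiples of about 1.6 to 1.8 and 3.3 to 3.9, are scenarios. They rest on an observed 0.55, 20% loss in the intervention arm, assumed dropout counts and control dropouts like control completers. It would be tempting to read them as what the plan's β3 would become, but they are not. β3 is a post-versus-pre coefficient that also draws on the delayed arm's crossover at 6 months, whereas the scenarios are simple 3-month contrasts between arms. The consequence falls mainly on the effect size carried into the later trial, so this is worth correcting but does not undermine the pilot's feasibility aims.

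**What to change.** In section 7.7:

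1. State that the mixed model fitted by likelihood to all available waves is the main analysis, and describe the existing comparison as a check on baseline missingness only.
2. Add a delta-adjusted tipping-point analysis. Impute missing 3- and 6-month counts by arm from baseline count, age and earlier follow-up counts, adding app-use paradata for periods when that arm has access. Multiply the imputed intervention-arm counts by factors from 1.0 upward and refit the same model.
3. Continue until the estimated ratio reaches 1.0 or the planning effect size changes materially. Report that factor beside the effect size carried into the future trial.

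Do not cap the factor at 2.0. If imputed counts average 0.55 of control, a factor of 2.0 takes them only to 1.10 times control. Reaching 1.5 times control needs 1.5/0.55 = 2.7, and a ratio of 1.0 with 8 of 40 lost needs 2.80/0.55 = 5.1. Imputation without the delta step would not be enough, because it largely repeats the mixed model's assumption.

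The cost is analysis programming; every input is already being collected.

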8.1 HUMAN SUBJECTS PROTECTIONS

8.2 Informed Consent and Assent

The study plan, advertisements, or recruitment letters, lay description of the study, and all consent forms will be submitted to the IRB following proposal acceptance and prior to study initiation. MPI, [name], will be responsible for obtaining IRB approval for this study. Recruitment for study participation will occur following IRB approval. The MPIs will delegate study task to research staff including determining eligibility for inclusion, explaining the purpose of the study, answering any questions, and obtaining e-assent/consent from the participants. Individuals who agree to participate will sign an e-assent/consent form. Potential risks and strategies for risk management will be carefully explained as part of informed e-assent/consent procedures. All HIPAA requirements will be applied to this study.

8.2.1 Consent and Assent Process

Written informed e-assent will be obtained from study participants under age 18. Participants at age 17 will be considered children for purposes of study activities. As such, they will complete informed assent for these portions of the study. Study participants ages 18 and above will provide written informed consent. If a respondent asks any questions about the study, an on-site research assistant will clarify or answer questions. The participant's ability to not respond to any study questions and/or terminate participation at any time will be stated clearly in consent forms.

8.2.2 Parental consent

Consistent with our prior studies in this population, we will not require parental consent for study enrollment. Parental consent may decrease participation rates because some youth (17-year-olds) will fear that they may be "outed" as a result of participation. Disclosure of sexual orientation or gender identity may place participating youth at risk for parental harassment, abuse, or expulsion from the home. The nature and scope of the proposed research do not pose more than "minimal risk" to participants, or that "the probability and magnitude of harm or discomfort anticipated in the research are not greater in and of themselves than those ordinarily encountered in daily life or during the performance of routine physical or psychological examinations or tests" (45 CFR Part 46.102). Study measures are standard in this population, as are waivers of parental permission for survey and interview studies.

8.2 Waiver of Parental Written Consent and Screening Procedure Written Consent

Each study site has experience conducting HIV prevention research with minors. We will be applying for a waiver of written informed consent from the parents of study participants because the involvement of children in this research meets the criteria for waiving parent permission (45 CFR 46.116(d)). The study qualifies for a waiver of parental consent as the following criteria are met in this study:

- The research involves no more than minimal risk to the subjects - The study does not place the patient at any additional risk than using their smartphones during their everyday lives.
The only other risk to participants is a breach of their protected health information, and we have put systems in place to protect their identity.
- The waiver or alteration will not adversely affect the rights and welfare of the subjects - If parents are required to consent their children then this may present a breach of confidentiality related to participants' sexuality and sexual behaviors.
- The research could not practicably be carried out without the waiver or alteration - If consent is required from parents then this may jeopardize the confidentiality of our study participants' health behaviors and may place study participants at increased risk of adverse outcomes associated with disclosure of their sexual orientation to their parents. Past research has shown a higher risk of familial childhood maltreatment among lesbian, gay, and bisexual individuals than among heterosexual individuals.
- Whenever appropriate, the subjects will be provided with additional pertinent information after participation - All study subjects will be given a copy of the written assent form which will include contact information of our study team as well as referral information.

To compensate for the waiver of parental consent, participants receive the described formal individual assessment of capacity to consent (above) to ensure their understanding of study

goals, procedures, and risks from disclosure of sensitive information. Consistent with national policy recommendations from the Society for Adolescent Medicine, requiring parental permission for the proposed study would have a number of possible negative effects, including: (1) reducing the validity of the findings by effectively eliminating potential participants unwilling to share permission forms with their parents/guardians; (2) increasing risk to some youth whose parents have a negative response to the material in the permission forms that would (correctly) suggest their child has a minority or alternative sexual orientation; and (3) contributing little to actual subject protection, given the minimal risk of study participation.

We are also requesting a waiver of documentation of consent for online screening procedures. The screening information will only be kept electronically in REDCap, which is a secure, CUMC approved system.

8.3 Vulnerable Subjects: Protecting Against/Minimizing Potential Risk

8.3.1 Procedures in the event of a reactive HIV test.

In the event a participant has a reactive HIV test, study team members will counsel the participant regarding the meaning of their result. Specifically, the study team will reiterate with the participant that:

- Their result is a preliminary positive, and it is likely that they are infected with HIV,
- The preliminary positive result needs to be verified with confirmatory testing,
- They need to return for the results of their confirmatory testing, and
- Resources for counseling and referral to care are available to them.

The participant will be referred for follow-up testing and care. We have one physician and one nurse as part of our investigator team.

8.4 Risks

8.4.1 Overview of Potential Risks

There is no more than a minimal risk associated with any of the proposed study activities. The study activities meet the general definition found in Subpart A (46.102) that the probability and magnitude of harm or discomfort anticipated in the research are not greater in and of themselves than those ordinarily encountered in daily life or during the performance of routine physical or psychological assessments or tests. The risks of participating in this study are few. Potential risks are those related to venipuncture, discomfort with study interview questions, and potential breaches of confidentiality. It is possible that certain questions on the survey may make participants feel uncomfortable, but participants are free to decline to answer any questions. Additionally, clinical study sites have co-located mental health and/or counseling services that may be consulted should a participant enter crisis. Participation in research can involve loss of privacy. All study data will be maintained on Columbia University Irving Medical Center (CUIMC) and Lurie Children's Hospital servers that are secure and HIPAA compliant. All signed consent forms, study data, and payment receipts used in this study will be kept in locked files at both sites which only the investigators can access. We will also receive a Federal Certificate of Confidentiality which will protect against attempts by law enforcement or other government

agencies to access our data.

8.4.2 General Risks

There may be risks or discomforts in participating in this study. Participants may feel uncomfortable with the HIV prevention information that is provided and completing some questions in the survey. Participants may skip any HIV information or questions that may make them feel uncomfortable or stop the research procedure. People around may observe participants using the MyPEEPS Mobile application. If participants are concerned about people seeing them use of MyPEEPS Mobile, it is important that they access the application in private location.

